Time Period	Treatment Assignment	Study Drug Administration Day	Treatment Period													
			Wk 1	Wk 2	Wk 3	Wk 4	Wk 5	Wk 6	Wk 7	Wk 8	Wk 9	Wk 10	Wk 11	Wk 12	Wk 13	Wk 14
Study Day		1 ^a	8	14	21	28	35	42	49	56	63	70	77	84	91	98
Visit Window (Days)		NA	±3	±5	±3	±5	±3	±5	±3	±5	±3	±5	±3	±5	±3	±3
Study Procedures																
Quality of Life (FACT-BMT, EQ-5D-5L, EQ-5D-Y, EQ-5D-Y Proxy Version 1) ^b		X												X		X

Abbreviations: AdV = adenovirus; ALT = alanine aminotransferase; AST = aspartate aminotransferase; ; β-HCG = beta human chorionic gonadotropin; BKV = BK virus; CBC = complete blood count; CMV = cytomegalovirus; EBV = Epstein-Barr virus; ECG = electrocardiogram; ET = Early Termination Visit; GGT = gamma-glutamyl transferase; GVHD = graft versus host disease; HBV = hepatitis B virus; HCV = hepatitis C virus; HIV = human immunodeficiency virus; HHV-6 = human herpesvirus 6; I/E = inclusion and exclusion; IVIG = intravenous immunoglobulin; JCV = JC virus; LFT = liver function test; NA = not applicable; PBMC = peripheral blood mononuclear cell; SoA = Schedule of Activities; VST = virus-specific T cell; Wk = week

Note: Visits may be done via a home health visit as agreed with the Sponsor. Please see the Study Manual for more information.

^a Unless noted otherwise, Day 1 procedures must be performed within 72 hours prior to study treatment administration.

^b Dosing day may be up to +7 days with Sponsor approval.

^c Adverse event monitoring should include the collection of all adverse events through the treatment period in all patients, including those who have discontinued study treatment but are continuing in the study. For patients who have discontinued, only drug-related SAEs and SAEs leading to death will be collected until Week 26.^d After treatment assignment, a targeted physical exam may be performed if a patient has any complaints. Post-HCT, the skin should be examined, even if the patient has no complaint, for evidence of rash/acute skin GVHD.

^e Includes body temperature, blood pressure, heart rate, O₂ saturation, and respiration rate and will be measured after resting for 5 minutes. After treatment assignment, vital signs should be performed during and after infusions and if targeted physical examination is performed.

^f Performed within 1 hour after study treatment administration and at the end of study or early termination visit, which are listed in the SoA for the Short-term Follow-up period (Table 3).

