^b Adverse event monitoring should include the collection of all adverse events through follow-up in all patients, including those who have discontinued study treatment but are continuing in the study. Positive pregnancy and partner pregnancy information up to 90 days after last study drug administration will be collected.

^c Viral loads of AdV, BKV, CMV, HHV-6, and JCV in plasma and in PCMBs for EBV will be measured and evaluated at the central lab. Additional post-infusion samples may be collected if clinically indicated. If patient develops any clinically significant infection of AdV, BKV, CMV, EBV, HHV-6, or JCV at any point during the study periods, infection assessments should be completed prior to initiating standard of care therapy (see [Section 8.3](#)).

^d Patient peripheral blood mononuclear cells will be assessed for the presence of virus-reactive T cells using enzyme-linked immunospot.

^e The infection assessment will be performed for all patients who require either treatment for disease or initiation of preemptive therapy during both the primary study period and the follow-up period through Week 26 ([Section 8.3](#)). It is very important to ensure that all procedures, as outlined in the SoA, are performed immediately prior to the initiation of treatment of viral diseases or initiation of preemptive therapy (ie, on the day anti-viral therapy is initiated). Most importantly, a plasma sample for AdV, BKV, CMV, HHV-6, and JCV and a PCMB sample for EBV for PCR testing at the central laboratory should be collected. After developing an infection, such patients will continue to be followed in the study and complete all remaining visits through Week 26.

^f Assessment of quality of life (using FACT-BMT, EQ-5D-5L, EQ-5D-Y, and EQ-5D-Y Proxy Version 1questionnaires, as age-appropriate) should be completed prior to any study procedures at this visit.

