8.5.1. Time Period and Frequency for Collecting AE and SAE Information

- All AEs and SAEs will be collected at the time points specified in the SoA ([Section 1.3](#)) from signing of informed consent until study participation is complete.
- Medical occurrences that begin before treatment assignment but after obtaining informed consent/assent will be recorded as Medical History/Current Medical Conditions, not as AEs.
- All SAEs will be recorded and reported to the Sponsor or designee immediately and under no circumstance should this exceed 24 hours, as indicated in Appendix 3 ([Section 10.3](#)). The Investigator will submit any updated SAE data to the Sponsor within 24 hours of it being available.
- Investigators are not obligated to actively seek information on AEs or SAEs after conclusion of the study participation. However, if the Investigator learns of any SAE,

including a death, at any time after a participant has been discharged from the study, and he/she considers the event to be reasonably related to the study intervention or study participation, the Investigator must promptly notify the Sponsor.

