1 INTRODUCTION

The purpose of this Statistical Analysis Plan (SAP) is to provide a description of the statistical methods to be implemented for the analysis of data from the Phase 2 open label (OL) cohort of Protocol P-105-202. All the patients in the Phase 2 OL were enrolled, treated, and followed under Protocol Amendment 2 dated 7 April 2021. Data were collected under Protocol Amendment 2 Schedule of Activities ([Appendix 2](#)). The analysis will be based on Protocol Amendment 4 dated 19 October 2021. In addition, the clinically significant infections or episodes of end-organ disease were determined by the clinical investigators in Phase 2. [REDACTED]

The SAP will be finalized prior to Phase 2 database lock. Any deviations from the SAP after database lock will be documented in the final Clinical Study Report (CSR) for the Phase 2 OL cohort. [REDACTED].

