3.5.1 Adverse Events (AEs)

All AEs will be coded to system organ class and preferred term using MedDRA. Treatment emergent adverse events (TEAEs) are defined as an AE with onset or worsening on or after the first dose of study treatment through the end of study (i.e., Week 26).

An overall summary of AEs will be provided with the number and percentage of patients who experienced at least 1 AE or TEAE in the following categories:

- Any TEAEs
- Any TEAEs by severity
- Any treatment-related TEAEs
- Any AEs of special interest (AESIs)
- Any treatment-emergent AESI (TEAESIs)
- Any treatment-related TEEAESIs
- Any serious AEs (SAEs)
- Any treatment-emergent serious AEs (TESAEs)
- Any treatment-related TESAEs
- Any TEAEs leading to discontinuation of study treatment
- Any TEAEs leading to discontinuation of study
- Any AEs leading to death

The numbers and percentages of patients will also be presented by system organ class (SOC) and preferred term (PT) for each of the TEAE categories in the summary. Patients with multiple AEs will be counted only once per SOC and PT. The number and percentage of patients with TEAEs will be tabulated by PT and by the highest CTCAE Grade.

Listings will be presented specifically for any AEs, deaths, SAEs, and TEAEs leading to discontinuation of study treatment and study.

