3.5.2 AEs of Special Interest

Adverse events of special interest (AESI) include infusion-related AEs, GVHD, and cytokine release syndrome (CRS). These AESIs will be reviewed by the DSMB as per the DSMB Charter. Criteria for acute and chronic GVHD and CRS can be found in Protocol Appendix 5 and 6, respectively. The number and percentage of patients who had the AESIs will be summarized:

- Severity and incidence of acute GVHD
- Severity and incidence of chronic GVHD
- Severity and incidence of CRS
- Severity and incidence of infusion-related AEs
- Severity and incidence of graft failure

Subgroup analyses may be conducted for the severity and incidence of acute GVHD by HLA type and the number of HLA matching.

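### Two rules conflict on AE collection after Week 14 in patients who stop study drug but stay in the study, so TEAE and new-onset GVHD incidence through Week 26 may be undercounted

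*Protocol*

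**What the plan says.** Footnote c to Protocol Tables 2 and 3 has two sentences. The first requires "collection of all adverse events through the treatment period in all patients, including those who have discontinued study treatment but are continuing in the study". The second reads: "For patients who have discontinued, only drug-related SAEs and SAEs leading to death will be collected until Week 26". Protocol 4.1 repeats both, in a list of what is collected while patients remain in the study to Week 26.

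The follow-up schedule says something else. Table 4 footnote b: "Adverse event monitoring should include the collection of all adverse events through follow-up in all patients, including those who have discontinued study treatment". Protocol 8.5.1 collects all AEs and SAEs "from signing of informed consent until study participation is complete", and Protocol 10.3.4 requires every SAE from treatment assignment until participation is complete (or the event resolves, if sooner) to be reported, not only related or fatal ones.

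The SAP inherits both rules. Its Introduction states: "Data were collected under Protocol Amendment 2 Schedule of Activities". That schedule, in SAP Appendix 2, carries footnote c under Tables 6 and 7 and footnote b under Table 8. SAP 3.5.1 defines a TEAE as onset or worsening "on or after the first dose of study treatment through the end of study (i.e., Week 26". For special-interest events, SAP 3.5.2 says: "The number and percentage of patients who had the AESIs will be summarized". Both summaries use the Safety Population, and SAP 3.1.5 analyses data as observed without imputation. Nothing in the SAP makes an exception for patients who discontinued.

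**The concern.** A site could follow either rule for a patient who has stopped infusions but still attends visits. Under the narrow rule, a new event after Week 14 that is not serious, or is serious but judged unrelated and not fatal, would not be recorded. The patient would stay in the Safety Population denominator and count as event-free to Week 26, so the error can only lower the reported incidence.

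The patients concerned are not a random subset. Protocol 7.1 ends infusions for severe acute GVHD, related Grade 3 to 4 non-hematologic AEs, persistent Grade 3 or 4 CRS, or therapy for relapse. Chronic GVHD is the outcome most exposed: it is an AESI, and Table 4 has neither a GVHD row nor a physical examination row, so a new case in follow-up appears to reach the data mainly through AE reporting.

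**Working it through.** The documents give no AE rate, discontinuation rate or sample size derivation for this point, so there is no plan figure to reproduce. The check is a comparison of the texts, followed by illustrative arithmetic.

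**1. The rules side by side, for a patient off study drug but still in the study**

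| Source | Weeks 1 to 14 | Weeks 14 to 26 |
|---|---|---|
| Tables 2 and 3 footnote c, Protocol 4.1, SAP Tables 6 and 7 (if *discontinued* means from drug) | all AEs | drug-related or fatal SAEs only |
| Table 4 footnote b, SAP Table 8 | – | all AEs |
| Protocol 8.5.1 | all AEs and SAEs | all AEs and SAEs |
| Protocol 10.3.4 | all SAEs | all SAEs |

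The rules agree to Week 14. The conflict is confined to follow-up.

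**2. Which reading of *discontinued* is better supported?** Three points favour *from drug*. The preceding sentence of footnote c is about patients off treatment who continue in the study. In 4.1 the sentence describes what is collected from patients who remain to Week 26. Patients who leave the study have an early termination visit at that point (Protocol 7.2 and 7.3), so collection to Week 26 fits them poorly. The term is nonetheless undefined.

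**3. Exposed window.** Protocol: Day 98 to Day 182, (182 − 98)/182 = 84/182 = 46% of the time to Week 26. With the SAP's nominal days: (183 − 99)/183 = 84/183 = 46%.

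**4. Possible size if the narrow rule was applied.** N is 25 to 35 (SAP 2.2.3). The other inputs are assumptions, not in the documents:

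- d, share who stop drug early but stay in the study: 10% to 40%
- q, chance that a patient's first event of a given type falls in Weeks 14 to 26: 5% to 30%
- m, share of those events that are neither drug-related SAEs nor fatal SAEs: 50% to 100%

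Expected patients missed per event type = N × d × q × m. Loss in the cohort rate = d × q × m. Loss in the rate among early stoppers = q × m.

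- Low end: 25 × 0.10 × 0.05 × 0.5 = 0.06 patients; 35 × 0.10 × 0.05 × 0.5 = 0.09; cohort loss 0.25 points; 2.5 points among stoppers.
- High end: 25 × 0.40 × 0.30 × 1 = 3.0 patients; 35 × 0.40 × 0.30 × 1 = 4.2; cohort loss 12 points; 30 points among stoppers.
- In between (d = 20%, q = 15%, m = 100%): 25 × 0.20 × 0.15 = 0.75 patients; 35 × 0.20 × 0.15 = 1.05; cohort loss 3 points; 15 points among stoppers. With 5 or 7 stoppers, the chance of missing at least one patient is 1 − 0.85^5 = 0.56 or 1 − 0.85^7 = 0.68.

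If all AEs were collected to Week 26 in everyone still in the study, the loss from this source is zero.

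**The case against.** The best defence is that *discontinued* in the second sentence of footnote c means discontinued from the study. The first sentence deals with patients off drug who continue, and the second drops that qualifier, which can be read as a contrast. The protocol also provides limited reporting after departure: 8.5.1 asks for related SAEs, including deaths, that the investigator learns of after discharge, and 10.3.4 asks for related SAEs after participation ends. On this reading there is no clash with Table 4 footnote b. The reading is possible, but the placement of the sentence in 4.1 weighs against it.

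It is also fair that footnote c belongs to the Week 1 to 14 tables, while Table 4 schedules AE review at Weeks 18, 22 and 26 and expressly includes patients off treatment. A site working from Table 4 would collect everything. That lowers the chance of loss, but 4.1 repeats the narrow sentence outside any table.

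Other points stand as limits. Patients discontinued for GVHD or CRS are followed until symptoms resolve (footnote l). Toxicities that end dosing under 7.1 are followed to resolution or the end of participation, and SAEs and AESIs already reported are followed under 8.5.3. A reader might infer that all GVHD in early stoppers is at risk, or everything after the last infusion. The documents do not support that: only new-onset events after Week 14 are exposed.

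**Conclusion.** The contradiction is real and sits in the schedule under which the open-label data were collected. The supported conclusion is conditional: if sites applied the narrow sentence to patients off drug but still in the study, TEAE and AESI incidence through Week 26 may be undercounted in early stoppers for Weeks 14 to 26, chiefly for new-onset chronic GVHD.

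A reader might infer that the Week 26 rates *are* undercounted. No section shows which rule sites used, so that does not follow. Nor can one figure for the shortfall be defended: the 0.25 to 12 point range rests wholly on assumed stopping rates, event risks and capture, and its upper end takes every exposed event as lost, although related or fatal SAEs are collected even under the narrow rule.

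The point should be resolved before the Week 26 safety tables are interpreted.

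**What to change.** In the protocol, define *discontinued*. Reconcile footnote c of Tables 2 and 3 and Section 4.1 with Table 4 footnote b and 8.5.1, so that all AEs are collected through Week 26 for every patient still in the study. State that any restricted SAE collection applies only to patients who have left the study.

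Rewording recovers nothing for open-label data already collected, so the SAP should state which rule sites followed. If collection was restricted, keep the Week 26 table, because dropping it would set aside valid follow-up data from patients who completed treatment. Add TEAE and AESI summaries either limited to Week 14, where the rules agree, or using person-time that ends when full collection ended, and flag the restricted patients.

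The cost is wording, a little more AE entry at visits already scheduled, and one extra table.

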2. INTRODUCTION

ALVR105 (also known as Viralym-M and formerly known as ALVR-105) is a cellular therapy consisting of third-party, multivirus-specific T cells with specificity for adenovirus [AdV], BK virus [BKV], JC virus [JCV], human herpesvirus 6 [HHV- 6], Epstein-Barr virus [EBV], and cytomegalovirus [CMV] in [REDACTED] [REDACTED]

AlloVir is developing ALVR105 (also known as ALVR105, formerly ALVR-105), a novel multivirus-specific cellular therapy, to treat or prevent a number of serious, virus-associated causes of morbidity and mortality after allogeneic HCT, including those caused by infection or reactivation with BKV (and the related polyomavirus JCV), CMV, HHV-6, EBV, and AdV.

2.1. Study Rationale

This is a phase 2 study to evaluate the efficacy and safety of ALVR105 for the prevention of clinically significant adenovirus (AdV), BK virus (BKV), cytomegalovirus (CMV), Epstein-Barr virus (EBV), human herpesvirus 6 (HHV-6) and JC virus (JCV) infections and/or disease in patients at high risk for these viruses following allogeneic hematopoietic cell transplant (HCT). In healthy, immunocompetent individuals, T cell immunity plays a central role in defending against viruses. In HCT recipients, the use of potent immunosuppressive regimens (and subsequent associated immunocompromise) leaves patients susceptible to severe viral infections. In approximately 90% of allogeneic HCT patients, the suppressed immune system allows viruses that were previously in a latent, quiescent state to reactivate and more than 60% of allogeneic HCT patients experience a reactivation of more than one virus, including BKV, CMV, AdV, EBV and HHV-6 ([Hill 2017](#)). Viral infections result in devastating morbidities and have become leading etiologies for transplant-related mortality. There is no approved anti-viral agent that can prevent such potentially devastating single and/or multi-virus infection(s) as a single therapy. Some off-label use of antiviral agents is associated with significant toxicities (notably myelosuppression and renal toxicity which might impede their use) and the emergence of drug- resistant viruses.

As delay in the recovery of endogenous virus-specific T cells (VST) is clearly associated with viral reactivation and disease in these patients, cellular immunotherapy to restore viral-specific immunity has been investigated as a potential therapeutic option. The development of ALVR105 for the prevention and preemptive treatment of AdV, BKV, CMV, EBV, HHV-6, and/or JCV infections represents an unmet medical need.

2.2. Background

During the period of immune recovery after allogeneic HCT, viral infections and reactivations, which are normally controlled by T cell immunity, are an important cause of morbidity and mortality. The risk for infection is dictated by a number of factors, including the degree of immunosuppression and the immune status of the donor. Reactivation of latent viruses such as CMV and BKV, or primary infection with a virus such as AdV, has become increasingly prominent. In a study at a large US HCT center, in approximately 90% of allogeneic HCT patients, the suppressed immune system allows viruses that were previously in a latent, quiescent state to reactivate and more than 60% of allogeneic HCT patients experience a reactivation of more than one virus, including BKV, CMV, AdV, EBV and HHV-6 ([Hill 2017](#)). In another recent study of infections following haploidentical allogeneic HCT, Slade, et al documented that 72% of patients

experienced at least one severe viral infection (Slade 2017). Fifteen percent of patients developed CMV infection despite prophylaxis, and 19% developed BK virus-associated –hemorrhagic cystitis. One of 3 children is reported to have an AdV infection within 6 months following allogeneic HCT (Sedláček 2019). Progression to AdV disease is associated with significant morbidity and mortality rates of up to 50% (Zecca 2019). Similarly, Mulanovich and colleagues (2011) reported that, among patients receiving either cord blood or T-cell depleted transplants, viral infections were frequent and the most common cause of death in both groups. Even among T cell-replete transplants using the post-cyclophosphamide protocol, Crocchiolo (2015) reported the incidence of viral infections to be 70%, with CMV and BKV being the most frequent and the most clinically threatening etiologies. The increased risk of mortality in the first 60 days post-transplant was approximately 18 times greater for patients with a CMV viral load ≥ 250 IU/ml (Green 2016).

2.2.1. Overview of Nonclinical Studies with ALVR105

Consistent with guidance from the United States Food and Drug Administration (FDA), AlloVir proceeded to clinical studies following completion of in vitro studies. No nonclinical animal pharmacology, pharmacokinetic, or toxicology studies of ALVR105 have been conducted or are planned. For additional information related to nonclinical studies with ALVR105, see the Investigator's Brochure.

2.2.2. Overview of Clinical Studies with Virus-Specific T Cells

2.2.2.1. Results of the CHARMS Study with Third Party-Derived Multivirus-Specific T Cells, ALVR105

To investigate the safety and clinical efficacy of ALVR105, a multivirus-specific T cell product reactive for BKV, AdV, HHV-6, EBV, and CMV generated from third-party, healthy, eligible donors, a Phase 1/2a clinical study was conducted in recipients of allogeneic HCT with drug-refractory infections with ≥ 1 of the 5 viruses targeted by ALVR105 (Tzannou, 2017). In this study, patients received a single IV infusion of 2×10^7 partially HLA-matched ALVR105 cells/m², with the option to receive a second infusion after 4 weeks (actual range 14 days to >6 weeks) and additional infusions at biweekly intervals thereafter. Therapy with standard antiviral medications could be continued at the discretion of the treating physician (Tzannou, 2017).

A total of 58 patients with drug-refractory infections following allogeneic HCT were infused with ALVR105 cell lines matched at 1 to 6 HLA antigens; 54 of these patients completed study treatment and the initial 28-day safety follow-up (the first 38 patients to complete the study are reported in Tzannou et al, 2017. Of the 71 total infections treated, 25 (35.2%) infections were BKV and 24 (33.8%) infections were CMV. Of the 58 patients who were treated (one of whom had 2 courses of treatment), 48 patients were treated for a single virus, 10 patients were treated for 2 viral infections, and 1 patient was treated for infections by 3 different viruses.

All infusions were well tolerated. None of the patients developed cytokine release syndrome (CRS). In the weeks after infusion, 1 patient developed recurrent Grade 3 gastrointestinal (GI) GVHD following rapid systemic corticosteroid taper, and 8 patients developed recurrent ($n = 4$) or de novo ($n = 4$) Grade 1 to 2 skin GVHD, which resolved with the administration of topical treatments ($n = 7$) and reinitiation of systemic corticosteroids after taper ($n = 1$). Between 3 and 6 months after infusion, 2 patients experienced a flare of upper GI GVHD, which resolved after a brief systemic corticosteroid course.

Fifty-four (93%) of 58 evaluable patients had either a partial or complete clinical or virological response (either PR [defined as >50% reduction in viral load, or >50% improvement of clinical signs and symptoms] or CR [defined as return of the viral load to the normal range and resolution of clinical signs and/or symptoms]); no response was observed in 2 patients with AdV, and 1 each with CMV and HHV-6. Of note, all 23 patients with BKV-associated hemorrhagic cystitis (HC), 2 of 3 patients with CMV colitis, the patient with CMV encephalitis (n = 1), the patients with AdV enteritis (n = 1) and AdV HC (n = 1), and 2 patients with HHV-6 encephalitis had improvement or resolution of symptoms within 6 weeks of treatment. In most responders (CR or PR), a post-infusion increase in the frequency of circulating VSTs was detected.

In addition to patients with post-HCT CMV, EBV, AdV, BKV, and HHV-6-associated infections, patients with JCV infections were also enrolled in this Phase 1/2 study. This decision was based on the identical nature of BKV and JCV T cell epitopes and on results of previous studies. More recently, it was demonstrated that partially HLA-matched third-party BKV-specific T cells could produce similar results in 3 immunosuppressed patients with progressive multifocal leukoencephalopathy (PML). Post-infusion, 2 patients experienced an alleviation of the clinical signs and imaging features of PML while the third patient had a reduction in JC viral load and stabilization of symptoms ([Muftuoglu 2018](#)) Given these promising results in the context of a complete lack of proven antiviral medications effective against JCV and the potentially devastating complications associated with JCV, patients with JCV infection will be included in the Phase 3 study.

